The DBS system implant procedure would be the same as for patients consented under the Humanitarian Device Exemption for clinical care of primary dystonia and typical off label use of DBS for secondary dystonia (IRB# 10-01285), except the electrodes will be placed in the thalamus instead of the globus pallidus. The infection protocol (IV antibiotics + 10 days of antibiotics post-op) is also different from usual clinical care.

Post-operative visit 1 and initiation of device use (12 days after surgery +/- 3 days)

- Record any Adverse Experiences and/or Review subject diary for adverse experiences and dosing compliance.
- Record changes to concomitant medications
- Perform abbreviated physical examination
- Perform and record vital signs
- Initial activation of DBS device
- Videotaped dystonia rating scales (BADS, BFMDRS) (prior to and following activation of DBS)

Once the patient's system is programmed, the patient will receive a hand-held device to identify if the system is on or off and to slightly modify their settings if their symptoms necessitate. Patients will be seen every two months for programming adjustments, but may be seen at any time during the study to optimize programming.

All of the above is standard of care for post-operative visit 1 except the videotaping of dystonia rating scales.

Post-operative (months 2-11): Visits every 8 weeks +/- 14 days after initial programming appointment for adjustments to DBS settings

- Record any Adverse Experiences and/or Review subject diary for adverse experiences and dosing compliance.
- Record changes to concomitant medications.
- Perform abbreviated physical examination.
- Perform and record vital signs.
- Dystonia rating scales (BFMDRS, BADS)
- Optimize stimulator settings for best clinical benefit
- At the Month 6 visit, we will administer the PedsQL, UPDRS II, and the Modified Ashworth Scale (when possible)

All of the above is consistent with standard of care, except the PedsQL and Modified Ashworth Scale at the 6 month visit

Post-operative month 12 visit: 52 weeks +/- 14 days from surgical date

- Record any Adverse Experiences and/or Review subject diary for adverse experiences and exclusionary medication use.
- Record changes to concomitant medications.
- Perform complete physical examination.
- Perform and record vital signs.
- Clinical rating scales of motor function (videotaped):
 - Burke-Fahn Marsden Dystonia Rating Scale (BFMDRS)
 - Barry Albright Dystonia Scale (BADS)

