Infection: We plan to increase the peri-operative antibiotic coverage to include methycillin-resistance staphylococcus. Additionally, we will add a 10 day post-operative course of oral antibiotics to our infection prevention regimen as this has been suggested to improve post-operative infection rates in these children.

Depression: As part of screening and recording of adverse events at each interim visit, we will ask the patient and/or caregiver if the patient has experienced mood changes. In the event of severe worsening of mood and/or suicidal ideation, the study doctor will refer to appropriate psychiatry services, urgently consult with the medical safety monitor and log as an SAE.

Speech: As part of screening and recording of adverse events at each interim visit, the subject and caregiver will be asked about speech changes. Speech will also be assessed as part of dystonia rating scales by the study team. If there are negative changes detected on either AE recording or dystonia rating scales, the DBS will be turned off briefly to determine if these changes are stimulation induced. If these changes are not resolved with programming adjustment, the formal speech testing done initially on neuropsychological testing will be repeated, and this will be recorded as an AE.

Cognitive Changes: As part of screening and recording of adverse events at each interim visit, if the patient or caregiver endorses subjective cognitive changes, neuropsychological testing will be repeated. If there are negative changes on neuropsychological testing that cannot be resolved by stimulation changes, the study doctor will consult with the medical safety monitor.

Weight gain: Body mass index (BMI) will be measured at every visit and monitored for changes. Changes to BMI that are not attributable to improvement in the patient's condition or normal growth will be logged as an adverse event.

Additional time: Study visits will be conducted in conjunction with usual clinical visits, when possible, to minimize the amount of extra time needed to participate in the study

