15.0 Data and Safety Monitoring Plan

15.2 * DATA AND SAFETY MONITORING PLAN: (REQUIRED)

All greater than minimal risk studies are required to provide a plan. Lack of an adequate plan is one of the most common reasons why IRB approval is delayed.

Instructions:

Describe the plan for monitoring data quality and participant safety. Key areas that should be included in the plan are:

- An explanation of the plan to monitor data collection, study progress, and safety
- A description of who will perform the monitoring and at what frequency (e.g., the PI only, a contract research organization, a Data and Safety Monitoring Board or Data Monitoring Committee, etc.)
- The type of data and events that will be reviewed (e.g., adverse events, breaches of confidentiality, unanticipated problems involving risk to participants or others, unblinded efficacy data, etc.)
- Procedures and timeline for communicating monitoring results to the UCSF IRB, the study sponsor, and other appropriate entities
- Assurance that the research team will adhere to the **UCSF IRB reporting requirements**

As appropriate:

- A plan for conducting and reporting interim analysis
- Clearly defined stopping rules
- Clearly defined rules for withdrawing participants from study interventions

The study participants will be followed bi-monthly for the first year and then as frequently as clinically indicated for the second year. Safety assessments will be done at every visit including vital signs, limited physical exam, safety check of the DBS device. Any Adverse Experience will be recorded and the subject diary will be reviewed to detect any adverse experiences. The Investigator will maintain constant vigilance over the study and review the data no less than on a monthly basis. The data will be presented and reviewed by the MSM at least every 6 months. Data will be presented and reviewed by the IRB annually.

Study stopping criteria are two or more patients with study related serious adverse events i.e. symptomatic intracranial hemorrhage, subdural hematoma, seizures, worsening neurological status, or death.

Subject stopping criteria would be (1) greater than 40% worsening on the Burke-Fahn-Marsden dystonia rating scale (BFMDRS) or the Barry Albright dystonia scale (BADS) that does not improve with programming changes (2) Depression that does not improve with programming changes or suicidality. Any patient that is withdrawn from the study will be followed as part of intention to treat analysis.

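### Does the Speech paragraph in 14.3 leave speech changes that resolve with reprogramming out of the adverse-event record?

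*Combined protocol and SAP*

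**What the plan says.** The Speech paragraph in section 14.3 (Minimizing risks) has two detection routes. The first is questioning: "As part of screening and recording of adverse events at each interim visit, the subject and caregiver will be asked about speech changes". The second is scoring: "Speech will also be assessed as part of dystonia rating scales by the study team". A negative change by either route leads to a brief switch-off to see whether stimulation is the cause. The last sentence then reads "If these changes are not resolved with programming adjustment, the formal speech testing done initially on neuropsychological testing will be repeated" and ends by saying that the testing "will be repeated, and this will be recorded as an AE".

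The general recording rules are elsewhere and carry no such condition. Section 7.9 lists, for post-operative visit 1 and for the visits in months 2 to 11, "Record any Adverse Experiences and/or Review subject diary for adverse experiences and dosing compliance". The month 12 list has a similar item. Section 15.2, the data and safety monitoring plan, says "Any Adverse Experience will be recorded and the subject diary will be reviewed to detect any adverse experiences". Section 15.4 sends all AEs to the medical safety monitor.

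The Cognitive Changes paragraph of 14.3 has a similar condition with a different consequence. For negative changes on neuropsychological testing "that cannot be resolved by stimulation changes, the study doctor will consult with the medical safety monitor".

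**The concern.** In the last Speech sentence, both the repeat testing and the AE entry depend on the change not resolving. A coordinator working from that paragraph alone could conclude that a change cleared by reprogramming needs no AE entry.

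That would matter for three reasons. Sections 14.1 and 14.3 both expect stimulation-induced dysarthria to disappear when stimulation is reduced or switched off, so the resolving case is the expected one. Safety and tolerability is the first aim in 7.3, and how often reversible speech effects occur bears directly on it. Section 13.3 notes that many of these patients have trouble with expressive language and speech, which may limit self-report and give the scale route more weight.

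Post-operative visit 1 is a concrete example. Its list includes "Videotaped dystonia rating scales (BADS, BFMDRS) (prior to and following activation of DBS"). A speech change that first appears on the second scoring and goes away when settings are adjusted in the same session would be both scale-detected and resolved. The documents do not define an adverse experience, and no sentence says that 15.2 takes precedence over 14.3. Two staff members could therefore classify the same event differently.

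**Working it through.** The plan has no figure to reproduce here. The check sets the texts side by side, followed by one piece of arithmetic for scale.

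**Step 1. Four cases under the Speech paragraph.**

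| Found by | Resolves with programming? | AE step in 14.3 (Speech) | Covered by 7.9 and 15.2? |
|---|---|---|---|
| Questioning | No | Stated | Yes |
| Questioning | Yes | Not restated, but found in the course of AE recording | Yes |
| Scale only | No | Stated | Yes |
| Scale only | Yes | None | Yes, if the change counts as an adverse experience |

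Only the fourth row depends on the general rule alone. To fall there, a change must be missed or unreported by the subject, the caregiver and the diary, be picked up on a scale, and then resolve.

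**Step 2. Do the texts conflict?** Section 15.2 covers any adverse experience. Section 14.3 names one circumstance in which an entry is made and does not say that entries are made only then. Both can be obeyed at once, and the result is that the event is logged. The wording in 7.9 is looser, because it joins AE recording and diary review with an and/or, so 15.2 is the firmer source.

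**Step 3. Which reading of the condition fits better?** The Cognitive Changes paragraph uses non-resolution to trigger escalation, not to decide whether something is an AE. Reading the Speech condition the same way, as the trigger for repeat formal testing, agrees with 7.9 and 15.2. The harmful reading needs a paragraph on mitigation to override the safety monitoring plan.

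**Step 4. What depends on the AE label?**
- The only analysis in 7.25 compares rating-scale scores before surgery and at one year. The AE label does not enter it.
- The subject stopping criterion in 15.2 for worsening dystonia uses the scale scores themselves and already requires that the worsening does not improve with programming.
- The study stopping criterion concerns serious events. A speech change cleared by reprogramming would not usually be one.
- The 5-working-day report in 15.4 needs a related event that is serious or unexpected. Speech disturbance is a listed risk in 14.1.
- The scale scores are kept. Under 15.2 the investigator reviews the data at least monthly and the medical safety monitor at least every 6 months.

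What could be lost is an AE label and the routine AE notice that goes with it.

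**Step 5. Size if staff ignored 15.2.** With 15 implanted (section 9.3), each patient whose only speech event went unlogged lowers the observed rate by 1/15 = 6.7 percentage points. To go further, let p be the true per-patient risk, s the share of changes seen only on the scales and r the share that resolve. The recorded rate is p(1 − s·r), and the loss is p·s·r. The documents give none of these values. Taking p from 10% to 30%, s from 10% to 50% and r from 50% to 100%, all assumed:
- smallest loss: 0.10 × 0.10 × 0.5 = 0.005, or 0.5 points
- largest loss: 0.30 × 0.50 × 1 = 0.15, or 15 points

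The width of this range shows how little the documents support any one value. If 15.2 is applied, the loss is 0.

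**The case for a change.** The strongest case for a change is that a specific instruction tends to be read as displacing a general one. Speech is the only paragraph in 14.3 that ties an AE entry to non-resolution; the weight-gain paragraph logs unexplained changes whether or not they resolve. Little else would classify the event. Formal speech measurement is listed at baseline but not in the month 12 battery (both lists are given as likely content), and the repeat test is itself triggered only by non-resolution. One sentence could separate AE recording from the resolution condition at almost no cost, in a 15-patient study meant to inform a larger trial.

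It stands that the sentence is loosely built and that a cross-reference to 15.2 would make it tidier. It also stands that section 13.3 makes weak self-report plausible. However, caregivers are asked at every interim visit, and nothing in the documents suggests that they miss a decline in speech. The visit 1 example relies on the order of items in a list, which does not fix the order in time, and AE recording is listed for that same visit. The AE form is not in the documents, so its guidance cannot be checked.

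The obvious firm remedy, logging every negative speech change on the scales, has its own cost. With no threshold it would turn rating variation and momentary effects during setting adjustment into AEs and could dilute the tolerability data. Whether a brief effect removed in the same session is an AE at all is a classification question on which reasonable trialists differ.

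**Conclusion.** The concern does not call for a change. This is a wording ambiguity in a mitigation paragraph, not a contradiction. The recording rule in 15.2 has no exception for events that resolve, and a study team following all the sections together would log the change. The gap is a detail that staff can fill sensibly, limited to changes seen only on a rating scale that resolve with reprogramming.

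Its size is zero if 15.2 is applied, and otherwise 6.7 percentage points of the observed speech-AE rate for each patient misclassified. Any larger total rests on assumed risks and shares that the documents do not give. The planned analysis and the scale-based stopping criterion do not use the AE label, and the other stopping and expedited-reporting rules would not usually be affected. The conclusion assumes that staff treat 15.2 as the governing rule and regard a real worsening of speech on a scale as an adverse experience; the documents do not state either point, but both are the ordinary reading.

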7.0 Research Plan and Procedures

7.1 This new consolidated section requests information about:

- Hypothesis
- Aims
- Study Design
- Background and Significance
- Preliminary Studies
- Procedures
- Statistical Methods
- References

Later sections include:

- Drugs and Devices
- Sample Size, Eligibility, and Subjects
- Recruitment and Consent
- Risks and Benefits
- Data and Safety Monitoring Plan
- Confidentiality, Privacy and Security
- Financial Considerations
- Qualifications of Personnel
- Other Approval and Registrations

7.2 HYPOTHESIS: Describe the hypothesis or what the study hopes to prove (Help Text updated 9/13):

Based on historical results of ventralis oral posterior (Vop) thalamotomy in secondary dystonia, Vop DBS will be safe and tolerable and will have improvements equal to or better than globus pallidus DBS in secondary dystonia in children and young adults.

7.3 AIMS: List the specific aims:

- Determine safety and tolerability of Vop stimulation in children and young adults with secondary dystonia
- Assess preliminary efficacy of Vop stimulation for reducing dystonia in children and young adults with secondary dystonia
- Assess preliminary effects of Vop stimulation on quality of life in children and young adults with secondary dystonia

7.4 DESIGN: Briefly describe the study design (e.g., observational, interventional, randomized, placebo-controlled, blinded, cross-over, cross-sectional, longitudinal, pharmacokinetic, etc.):

This is a single-center, open-label, phase I clinical trial to estimate the treatment effect size and to assess preliminary safety and tolerability of Deep Brain Stimulation (DBS) of the ventralis oralis posterior nucleus of the thalamus in children and young adults with secondary dystonia. Patients will be recruited from two movement disorders centers: UCSF Center for the Surgical Treatment of Movement Disorders at Mount Zion and the Pediatric Brain Center at Mission Bay. The study will be discussed with all patients and their families/caregivers who meet inclusion and exclusion criteria, and written informed consent will be obtained from those patients who wish to enroll in the study.

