9.0 Sample Size and Eligibility Criteria

9.1 ENROLLMENT TARGET: How many people will you enroll:

17

If there are multiple participant groups, indicate how many people will be in each group:

9.3 SAMPLE SIZE JUSTIFICATION: Explain how and why the number of people was chosen. For multi-site studies, this is referring to the number that will be enrolled across all sites:

This is a phase I pilot study of 15 participants to determine safety and tolerability as well as estimate effect size to inform planning of future larger trials that will test effectiveness. There is not sufficient data on the efficacy outcome measures to calculate sample size using statistical methods, thus the number of subjects was estimated based on a similar prospective study of DBS of globus pallidus (GPI) in adults with secondary dystonia in which a significant improvement was found using 13 subjects. We will screen up to 17 patients to achieve a total of 15 implanted.

9.4 * PARTICIPANT AGE RANGE: Eligible age ranges: (REQUIRED)

- 0-6 years
- 7-12 years
- 13-17 years
- 18-64 years
- 65+

9.5 * STUDY POPULATIONS: Data will be collected from or about the following types of people (check all that apply): (REQUIRED)

- Inpatients
- Outpatients
- Family members or caregivers
- Providers
- People who have a condition but who are not being seen as patients
- Healthy volunteers
- Students

- Staff of UCSF or affiliated institutions
- None of the above

9.6 * SPECIAL SUBJECT GROUPS: Check the populations that may be enrolled: (REQUIRED)

- Children / Minors
- Subjects unable to consent for themselves
- Subjects unable to consent for themselves (emergency setting)
- Subjects with diminished capacity to consent
- Subjects unable to read, speak or understand English
- Pregnant women
- Fetuses
- Neonates
- Prisoners
- Economically or educationally disadvantaged persons
- None of the above

If not already addressed in the Background and Significance questions in the Research Plan section or elsewhere, explain why it is appropriate to include the types of subjects checked above in this particular study:

The intervention is aimed at children and young adults because data from Deep Brain Stimulation (DBS) in other sites in the brain (globus pallidus) suggests that the earlier in the disease course DBS is performed the better the outcome. DBS of globus pallidus has been shown to be safe and effective in children as young as 7 years of age.

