14.0 Risks and Benefits

14.1 RESEARCH-RELATED RISKS: Check if your study involves any of these specific research-related risks to participants that may need to be disclosed in the consent form:

- For interventional studies, risk that the regimen may be more harmful or less effective than other available interventions
- Risks associated with radiation exposure for imaging studies specifically for research purposes
- Risks associated with the administration of contrast agent for imaging studies
- Risks associated with withholding of treatment or discontinuation of current treatment (e.g., washout period is required by the study protocol)
- For randomized, placebo-controlled trials, possible temporary or permanent health consequences from the deprivation of effective therapies during the placebo administration period
- For studies involving a sham surgical procedure, the risk that participants may experience increased morbidity without the possibility of benefit
- Risks associated with modification or extension of a surgical procedure primarily for research purposes (e.g. risks associated with prolonging anesthesia, time in the operating room, etc.)
- Risk of pain or physical discomfort caused by the research intervention
- Possible personal discomfort due to sensitive topics (stress, embarrassment, trauma)

* For any boxes checked above, describe how you will minimize these risks and discomforts, e.g., adding or increasing the frequency of monitoring, additional screening to identify and exclude people with diminished kidney or liver function, or modification of procedures such as changing imaging studies to avoid giving contrast agent to people who are more likely to suffer side effects from it, etc.:

(REQUIRED)

- Weight gain or cognitive impairment. This is a theoretical risk based on side effects reported from thalamotomies in prior research reports
- Stimulation induced dysarthria or weakness. This is a theoretical risk based on side effects reported from thalamotomies in this patient population. If these side effects occur, decreasing or turning off stimulation should eliminate them.

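### Section 14.3 logs a BMI change as an adverse event only if it is not put down to improvement or growth, so the log can undercount weight gain in patients judged improved

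*Combined protocol and SAP*

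**What the plan says.** - **Risk (14.1).** "Weight gain or cognitive impairment. This is a theoretical risk based on side effects reported from thalamotomies in prior research reports".
- **Measurement (14.3, weight gain).** "Body mass index (BMI) will be measured at every visit and monitored for changes".
- **Logging rule (14.3, next sentence).** "Changes to BMI that are not attributable to improvement in the patient's condition or normal growth will be logged as an adverse event". No size of change, growth reference, criterion for attribution or assessor is given.
- **General rule (15.2).** "Any Adverse Experience will be recorded". The term is not defined there.
- **Safety review (15.2, 15.4).** The investigator reviews data at least monthly and the medical safety monitor at least every 6 months. Adverse events are also reported to the monitor. Relatedness to study procedures is graded as definite, probable or possible.
- **Design and aim (7.4, 7.3).** "This is a single-center, open-label, phase I clinical trial", with no concurrent control arm described. The first aim is: "Determine safety and tolerability of Vop stimulation in children and young adults with secondary dystonia".
- **Size and ages (9.3, 9.7).** "This is a phase I pilot study of 15 participants to determine safety and tolerability". Patients are aged 7 to 25 at surgery.
- **Visit lists (7.9).** The post-operative lists include "Perform and record vital signs" and a physical examination. No list names height, weight or BMI. Section 6.2 allows some later visits by video.
- **Analysis (7.25).** Only the dystonia rating scales are covered.

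**The concern.** Whether an event occurred and what caused it are separate questions. Section 14.3 merges them, because a BMI change enters the adverse event log only after its cause has been judged.

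The improvement exemption is the more serious of the two. If stimulation reduces dystonia and the patient then gains weight, the gain is still a consequence of the treatment under test, yet the rule does not call for it to be logged. The exemption can remove events only in patients judged improved, so the possible loss depends on the efficacy outcome and runs in one direction.

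The growth exemption is sensible in principle for ages 7 to 25. Without a stated age- and sex-adjusted reference, two assessors could apply it differently to the same child.

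At stake is the reported frequency of weight gain. It bears on the safety aim and, through it, on the larger randomised trial that 7.4 says this study will help to design.

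**Working it through.** The plan states no figure for weight gain. The 15 patients in 9.3 were chosen by analogy with a 13-subject study, so there is nothing to reproduce. The check has two parts.

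**1. Does another provision bring a filtered change back?**

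| Provision | What it does for a BMI change put down to improvement or growth |
|---|---|
| 15.2, all adverse experiences recorded | Leaves a route for gain that a patient or caregiver reports as a problem; does not say how it fits with the narrower BMI rule |
| 15.4, adverse events sent to the safety monitor | Does not apply if the change was never logged |
| 15.2, six-monthly review by the safety monitor | Might show the BMI values; no BMI listing is specified |
| 15.4, relatedness grading | Shows that cause can be recorded after logging; applies to logged events |
| 7.25, statistical methods | No summary of BMI or adverse events |
| 7.9, visit lists | Do not name height, weight or BMI, although 14.3 promises BMI at every visit |

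Recovery is possible but not assured.

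**2. How large could the undercount be?** The documents supply only n = 15 implanted.

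- One filtered patient: 1/15 = 6.7 percentage points.

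Everything below rests on assumptions that are not in the documents:
- p: true share of patients who gain weight, 10% to 40%
- r: share of those who also improve, 30% to 70%
- a: chance that an improver's gain is attributed to improvement, 50% to 100%

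The growth exemption is left out.

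Logged rate = p × (1 − r × a).

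Share of true cases logged = 1 − r × a. It runs from 1 − 0.7 × 1.0 = 30% to 1 − 0.3 × 0.5 = 85%.

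Expected count = 15 × rate. Chance of an empty log = (1 − rate)^15.

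| p | Expected true count | Expected logged count | Chance of none, all logged | Chance of none, rule applied |
|---|---|---|---|---|
| 10% | 1.5 | 0.45 to 1.28 | 20.6% | 26.4% to 63.3% |
| 20% | 3.0 | 0.90 to 2.55 | 3.5% | 6.1% to 39.5% |
| 30% | 4.5 | 1.35 to 3.83 | 0.5% | 1.2% to 24.3% |
| 40% | 6.0 | 1.80 to 5.10 | <0.1% | 0.2% to 14.7% |

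Worked case: p = 20%, r = 50%, a = 100%. The logged rate is 0.20 × (1 − 0.50) = 0.10 and the expected logged count is 15 × 0.10 = 1.5. The chance of an empty log is 0.90^15 = 20.6%, against 0.80^15 = 3.5% if every case were logged.

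If 0 of 15 were logged, the one-sided 95% upper bound would be 1 − 0.05^(1/15) = 18.1%. That bound describes the logged rate. It would not cover the true weight-gain rate at the stated level if cases had been filtered out.

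The extreme is 3 true cases, all in improvers and all attributed to improvement. The log would then show 0/15 (exact two-sided 95% interval 0% to 21.8%) in place of 3/15 = 20% (4.3% to 48.1%). This needs r = a = 100%, beyond the r range above.

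**The case against.** The strongest defence is that nothing need be lost. BMI is measured at every visit, the investigator and the safety monitor review data on a schedule, and a reported problem can still enter under the general rule in 15.2. Weight gain is in neither the study nor the subject stopping criteria. Expected growth in a child is not an adverse event, and gain in an underweight patient may be welcome. On this view the paragraph needs only a small clarification.

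Much of this stands, and it rules out several stronger readings that a reader might infer:

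- **That weight gain is an established harm of stimulating this target.** Section 14.1 calls it theoretical and takes it from lesioning reports.
- **That the unmasked team programming the device makes the attribution.** This is plausible in an open-label trial, but 14.3 names nobody.
- **That 14.3 defines exempt changes as not adverse events.** It says which changes will be logged; the exclusion is implied.
- **That any gain in an improver can be dismissed.** The rule requires gain attributable to improvement, not gain that merely coincides with it.
- **That the safety data are lost.** If BMI is collected as 14.3 says, the log can be repaired later.

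The mismatch with 7.9 is minor in itself, but it matters here because later repair depends on those measurements.

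The defence does not answer the main point. Followed as written, the rule withholds a possible treatment consequence from the log according to the efficacy result, and no planned summary puts it back.

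**Conclusion.** The concern holds for the adverse event log. Section 14.3 makes logging of BMI change depend on attribution to improvement or growth, in an open-label trial whose first aim is safety, without a stated threshold, reference or assessor. Weight gain can be undercounted in patients judged improved, and the improvement exemption can bias the logged rate only downwards.

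The documents do not allow the undercount to be sized. The one figure they support is 6.7 percentage points per filtered patient. The 30% to 85% logged share rests wholly on assumed inputs. The fall from 3/15 to 0/15 is an assumed extreme, not an expectation.

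The BMI values should exist if 14.3 is followed, so this is a correctable weakness in recording and reporting. It does not show that the trial cannot assess weight gain. The correction is worth making because it is cheap and concerns a risk the plan itself singled out for monitoring.

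**What to change.** 1. **14.3.** Replace the attribution condition. Log every BMI change from baseline beyond a limit the sponsor sets in advance, whatever the presumed cause. Use an age- and sex-standardised BMI z-score for patients within the age range of the chosen growth reference, and percent change in BMI for older patients.
2. **Cause.** Record presumed cause, including improvement or growth, in its own field, and state who completes it. Keep the relatedness grading in 15.4 as it is.
3. **7.9.** Add height and weight to the baseline and in-person visit lists so that they match 14.3.
4. **7.25.** Add a descriptive summary of month-12 BMI change, on the applicable scale, for all implanted patients, shown alongside dystonia response.

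The cost is a wording change, a few case-report fields and one descriptive table, for a measurement already planned. The downside is that more events will be logged, some of them welcome weight gain. The baseline value and the cause field will identify these.
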